11.0 Statistical/Data Analysis Plan

11.1 Statistical Considerations:

List the statistical methods to be used to address the primary and secondary objectives, specific aims, and/or research hypotheses. Explain how missing data and outliers will be handled in the analysis. The analysis plan should be consistent with the study objectives. Include any sub-group analyses (e.g., gender or age group). Specify statistical methods and variables for each analysis. Describe how confounding variables will be controlled in the data analysis

Primary Outcome Measures: Analysis of the primary outcomes will follow the ITT principal. For each of the two outcomes, a linear regression model with covariates that include treatment group, the stratifying variables, and baseline value of the outcome will be used to compare the prazosin and placebo groups at 13 weeks. In addition, we will conduct a repeated measures analysis using data from the two points of follow-up (8 and 13 weeks). The repeated measure analysis will be conducted by comparing response profiles between prazosin and placebo groups. An initial comparison will be conducted using the general estimating equations (GEE) method of Liang and Zeger,⁹¹ which allows all observed data points for each participant. Secondarily, an analysis of covariance (ANCOVA) rate of change analysis will be done as a confirmatory or sensitivity analysis. Stratifying variables will be included as covariates in each model since they are factors in the stratification. It is anticipated that a retrieved dropout strategy will

result in a limited number of missing observations. For the GEE analysis no imputation strategy is required. For the ANCOVA analysis the missing data patterns will be evaluated between the treatment groups. If the patterns are similar and the magnitude of missing data is small, a conventional last observation carried forward (LOCF) imputation will be performed. If the amount of missing data is substantial and/or the patterns of missingness disparate, as an alternative to the traditional ANCOVA, the summary statistic method of Dawson⁹² will be employed. This method has been shown to be robust to non-ignorable missingness. The approach summarizes the response profile using a least square slope, and stratifies on the missing data pattern. We will also run analyses to assess the interactions between treatment group and gender.

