A completers analyses will be done in a similar fashion for the primary outcome measures, using only the cases that remained on protocol throughout the 13-week study drug period.

Secondary outcome measures: All secondary outcome measures (PSQI, CAPS, PCL-M, SIP, and biological markers) will be analyzed in a manner similar to that described above for the primary outcome measures. (We will also perform exploratory analyses in a similar manner on the CAPS symptom clusters and individual CAPS items to generate hypotheses about differential responsiveness to prazosin for AUD relative to response of individual PTSD symptom clusters/symptoms).

Procedures to minimize missing data: Although all efforts will be made to complete study visits in person, it may be necessary to obtain assessments by telephone. Attempts will be made to reach the participant by telephone. The following actions will be attempted (as appropriate per visit schedule): 1) adverse events will be assessed by telephone, 2) assessments shall be completed by telephone interview with the raters, 3) self-rated measures will be done by mail using prepaid envelopes, and 4) dispensing of study drug shall be done by traceable shipment. No-show, missed visits and actions taken will be documented in the study record.

11.2 Sample Size:

Sample Size Estimation: The power analysis is based on two types of preliminary data: the results of [name] study of prazosin for reduction of alcohol use in persons with AUD without PTSD and the preliminary results of our study of prazosin for combat trauma PTSD in active duty SMs without AUD in which we obtained the PACS. There were 19 completers in [name] pilot study. Standard drink units in the final month of the study drug period were 30.3 ± 32 (mean \pm SD) ($N=10$) in the prazosin group and 62 ± 58 ($N=9$) in the placebo group ($F=1.50$, $p=0.012$). There were 53 completers in the prazosin study for combat trauma PTSD in active duty SMs. The difference (delta) in PACS scores were -2.6 ± 5.8 ($N=27$) vs. -0.3 ± 3.3 ($N=26$) in the prazosin vs. placebo groups, respectively, $t=-1.74$, $p=0.04$ (one-tailed).

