We used these preliminary data to power for both the primary outcome measures, the alcohol use calendar (similar to the Time Line Followback from [name] Voice Response [IVR] Standard Drink Units [SDU] data) and the PACS (from [name] data). Using the SDU data gives us 97% power, 2-tailed at $\alpha=0.05$ with a sample size of 60 in each group (total $N=120$). Using the PACS data gives us 76% power, 2 tailed, at $\alpha=0.05$, and 85% power, one tailed, at $\alpha=0.5$, with the same sample size. We have conservatively powered because [name] used IVR methodology and data were from persons with AUD without PTSD, and [name] were from Service Members with PTSD without diagnosed AUD, to power adequately for not only Hypothesis 1 for prazosin efficacy for AUD, but also Hypothesis 2 to determine the effects of PTSD diagnosis on response to prazosin for treatment of AUD.

Assuming an approximately 40% dropout rate, we will randomize 200 participants to have 120 study completers.

11.3 Total number of subjects requested (including records and specimens):

300

11.4 If you are recruiting by study arm, please identify the arms of the study and how many subjects will be enrolled in each arm

randomize 200 on a 1:1 ratio prazosin or placebo

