11.5 Please provide a justification for your sample size

11.6 Data Analysis Plan:

Statistical Analysis: Baseline comparability between treatment groups will be evaluated with respect to entry criteria, as well as demographic characteristics and baseline symptoms and assessment measure scores. We will use summary statistics and graphical techniques, such as box plots, to compare the baseline characteristics of treatment groups. Prior to conducting the main analyses, we will do checks via *t*-test and Chi-square to evaluate whether the randomization procedures resulted in groups with meaningful differences with regard to demographic factors such as age and ethnicity, AUD and/or PTSD symptom severity, subjective impressions of alcohol's reinforcing effects, and alcohol craving (PACS). Should we identify significant differences on any of these parameters, they will be taken into account statistically through covariation procedures. Since randomization will be blocked on assignment to the stratifying variables, we do not anticipate differences across conditions in those variables. We will also evaluate whether there are systematic differences (again via *t*-test and Chi-square) with regard to the individual characteristics noted above among those randomized that do and do not complete the study. In addition, we will generate summary descriptive statistics for each of these different subgroups and the overall sample.

Secondary analyses: In addition to the major analyses designed to address the study aims, the following secondary analyses will also be conducted:

Treatment retention: Between group comparisons via Chi-square will be conducted to determine whether the prazosin condition was more likely to complete the medication phase of the study. Study completion will be operationalized such that study completers will have attended at least 10 of the 14 interim study visits and the visit at 13-weeks when study participation is completed. We will also use *t*-test to compare the number of study visits attended overall by the two groups.

Study drug compliance: We will report descriptive statistics for pill counts to determine adherence. We will use *t*-tests to compare medication compliance across the two study conditions. Since prior work shows that individuals on active medication with 80% or greater medication adherence have superior outcomes to non-adherent individuals,⁹³ participants who achieve $\geq 80\%$ adherence will be defined as adherent.

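### The ITT week-13 regression has no missing-data rule, so as written it drops everyone without a week-13 value; week-8 data could reduce the resulting bias

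*Combined protocol and SAP*

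**What the plan says.** Section 11.1 states the principle, "Analysis of the primary outcomes will follow the ITT principal", and for each of the two primary outcomes gives "a linear regression model with covariates that include treatment group, the stratifying variables, and baseline value of the outcome will be used to compare"; the comparison is prazosin against placebo at week 13. A GEE on weeks 8 and 13 is added. A rate-of-change ANCOVA comes third, as a confirmatory or sensitivity analysis.

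The missing-data text follows. It relies on retrieving dropouts, without further description, to "result in a limited number of missing observations. For the GEE analysis no imputation strategy is required". In the rate-of-change ANCOVA, missingness patterns are compared between arms. "If the patterns are similar and the magnitude of missing data is small, a conventional last observation carried forward (LOCF) imputation will be performed"; otherwise the Dawson summary-statistic method, built on a least-squares slope and stratified by missing-data pattern, takes over. A completers analysis is planned separately.

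Section 11.2 adds: "Assuming an approximately 40% dropout rate, we will randomize 200 participants to have 120 study completers". Section 11.6 (treatment retention) defines completion: "study completers will have attended at least 10 of the 14 interim study visits and the visit at 13-weeks".

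Some collection beyond routine visits is described:
- Section 11.1 allows telephone assessments for missed visits, and "self-rated measures will be done by mail using prepaid envelopes".
- Section 13.6 has the week-13 assessments done at early termination when the minimum dose is not tolerated.
- Section 10.1 mentions an early discontinuation visit.
- The alcohol calendar covers the time since the previous visit, whereas PACS is given only at baseline and weeks 8, 13 and 19 (section 10.2).

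**The concern.** Three analyses are listed and two have a missing-data rule. The one without is listed first and carries the ITT label. A regression on week-13 values leaves out anyone who lacks one, so its population is those observed at week 13, not those randomised. If the reasons for leaving relate to drinking or craving differently under prazosin and placebo, the remaining groups are no longer comparable. The estimate can then show an effect that is not there or hide one that is, depending on which arm loses its higher scorers.

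The plan's reassurance rests on retrieving dropouts. The text does not say whether participants who stop study drug are sought at weeks 8 and 13, or whether a score taken at early exit counts as week 13. PACS is the more exposed outcome: a later calendar contact can recover earlier drinking, but a missed PACS cannot be recovered.

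**Working it through.** **1. The plan's own figures.** 120 / (1 − 0.40) = 200, as stated. For power at 60 per arm, two-sided 0.05, normal approximation:
- PACS: difference 2.6 − 0.3 = 2.3; SD = √((5.8² + 3.3²)/2) = 4.72; power 76.1% (stated 76%).
- Drinks: difference 62 − 30.3 = 31.7; SD = √((32² + 58²)/2) = 46.84; power 96.0% (stated 97%).

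These are not in dispute. Power is set on completers only.

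**2. How many could be missing.** 0.40 × 200 = 80 non-completers, 40 per arm if equal. Under section 11.6 every completer attends week 13, and a non-completer may also have week-13 data. So 40% is an upper figure, and 15%, 25% and 40% are all examined.

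**3. Simulation under no treatment effect.** 100 per arm; 3000 runs, so Monte Carlo error near 5% is √(0.05 × 0.95/3000) = 0.4 points. The outcome is normal. Assumed correlations, which the documents do not give: baseline–week 8 0.5, baseline–week 13 0.45, week 8–week 13 0.7. For 40% missing, 20% are lost at random before week 8, then 25% of the rest by a logistic model in the week-8 score: 1 − 0.80 × 0.75 = 0.40. For 25% the steps are 12.5% and 14.3%; for 15%, 7.5% and 8.1%. Slopes per SD are given as placebo/prazosin.

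Two analyses are compared:
- Observed-case: week 13 on arm and baseline, using those with a week-13 value.
- Using week 8 under missing at random (MAR): fit week 8 on baseline and arm (arm effect a), then week 13 on baseline, week 8 and arm (coefficients c for week 8, d for arm). The week-13 effect is d + c × a.

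| Missing | Slopes | Observed-case bias / type I error |
|---|---|---|
| 15% | 1/0 | about 0.04 SD / 5–6% |
| 25% | 1/0 | about 0.06 SD / 7–8% |
| 40% | 1/0 | about 0.10 SD / 9–10% |
| 25% | 1/0.5 | 0.03 SD / 5.7% |
| 40% | 1/0.5 | 0.04 SD / 5.8% |
| 40% | 0.5/0 | 0.06 SD / 6.3% |
| 40% | 1/1 | 0.01 SD / 5.9% |
| 40% | 1/−1 (extreme) | 0.21 SD / 25.8% |

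With the same slope in both arms but 30% versus 50% missing, the bias is −0.06 SD and the error 6.1%. The MAR analysis gives 0.00 SD and about 5% in the 1/0 and 1/−1 cases.

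**4. The planned GEE.** At 40% missing with week-8-driven dropout and visit-specific terms, slopes 1/0 and 1/−1:
- Exchangeable working correlation: 0.00 SD / 5.7% and 0.01 SD / 6.0%.
- Independence: 0.10 SD / 9.2% and 0.21 SD / 27.2%, much as for the observed-case regression.

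The working correlation therefore decides whether the GEE helps, and the plan does not name it.

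**5. Dropout driven by the unseen week-13 score.** At 40% missing, slopes 1/0: observed-case 0.17 SD / 19.6%, MAR 0.11 SD / 11.3%. At 15%: 0.06 SD / 6.8% and 0.04 SD / 5.5%. Using week 8 reduces this bias but does not remove it.

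**6. Skewed drinks.** Gamma outcome with mean 62 and SD 58 (the placebo figures in section 11.2), 1500 runs, 40% missing, week-8-driven, slopes 1/0: observed-case 0.11 SD / 10.1%; MAR 0.00 SD with 4.7 to 4.8% error.

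**The case against.** The best textual defence is that a baseline-adjusted regression is itself an ANCOVA, so the LOCF/Dawson rule covers it. This is strained. Section 11.1 attaches the term to the rate-of-change analysis, and the fallback summarises a slope, which is not a week-13 value. At best the rule is ambiguous.

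The substantive defence is stronger. The plan compares missingness patterns between arms, has a pattern-stratified fallback for the ANCOVA, and runs a GEE on all observed data. With a non-independence working correlation that GEE already removes nearly all the week-8-driven bias. This stands: a wholly new method is not required. What remains is that the unprotected regression is listed first and the GEE is an addition with no correlation named.

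The size also depends on scenarios that the documents do not supply. Mild differences between arms, or 15% missing in one arm, do little harm.

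A reader might infer more than the documents support:
- That 40% of week-13 values will be missing. The figure is non-completion, and retrieval is partly described.
- That there is no retrieval or missing-data plan. There is one, but it is incomplete.
- That the false-positive rate is inflated as things stand. This needs dropout that relates to outcome differently by arm, which the documents neither predict nor exclude.
- That sections 13.1, 13.6 and 14.2 contradict one another on discontinuation. The mixed wording, from study treatment and from the study, lies within section 13.6; the other two refer only to the study.

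The visit schedule cited in section 10.1 is not in the text available here and may settle part of the follow-up question. It is unlikely to supply an analysis rule.

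**Conclusion.** The concern holds as an omission in the first-listed primary analysis, worth correcting because the remedy is cheap. As written, the week-13 regression is an observed-case analysis under an ITT label. The likely harm is modest: about 0.04 to 0.06 SD of bias and 5 to 8% type I error at 15 to 25% missing with one-arm dependence, about 0.10 SD and 9 to 10% at 40%, and close to none if the mechanism is the same in both arms. These figures rest on the assumed correlations and logistic slopes, and on missingness that the plan does not state. The claim that week-8 data remove the bias holds only for dropout explained by observed scores. Confidence is medium.

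**What to change.** **Analysis.** Make the main week-13 comparison a repeated-measures estimate on weeks 8 and 13 that includes all randomised participants. Any of these serves: a likelihood-based model, multiple imputation by arm using baseline and week-8 data, or the planned GEE with visit-specific treatment terms and a named non-independence working correlation. Replace LOCF as the small-missingness option, keep the Dawson method, and add a delta-adjusted or tipping-point analysis for dropout that depends on unseen scores.

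**Supporting clarification.** Say what retrieved dropout means: whether PACS and the calendar are sought at weeks 8 and 13 after study drug stops, and by which of the routes in section 11.1. Record early-exit scores as their own visit, and do not count them as week 13 without a flag. Reconcile the two discontinuation wordings in section 13.6 with each other and with sections 13.1 and 14.2.

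**Cost.** The analysis change is a short rewrite of section 11.1 and needs no new assessment, since week-8 data are already collected. It makes the main result rely on MAR, hence the sensitivity analysis. Extending retrieval would take real effort: the contact routes in section 11.1 include shipping study drug, so they appear written for participants still on study, and records access ends 30 days after early discontinuation (section 10.1).

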drink units per day and binge drinking days throughout the trial, which will serve as primary outcome measures.

- *The Penn Alcohol Craving Scale (PACS)*: A self-report paper-and-pencil instrument that assesses various dimensions of craving for alcohol and has been found to have good reliability and validity.⁸¹ The PACS will be administered at baseline and on weeks 8, 13 and 19, and will be used as a primary outcome measure to determine whether prazosin is associated with reductions in alcohol craving.
- *Alcohol Use Disorders Identification Test (AUDIT)*:⁸² A 10-item self-report questionnaire that has served as a screening instrument for alcohol problems in a number of different settings.⁸³ The AUDIT measures at least two factors, one related directly to alcohol consumption and the other to adverse behavioral effects of excessive consumption.^{84, 85} An advantage of the AUDIT is that it can delineate not just individuals likely to have an alcohol use disorder diagnosis but can place respondents on the full spectrum of alcohol misuse from no problem to hazardous drinking to dependence. The AUDIT has well supported reliability, validity, sensitivity, and specificity. The AUDIT will be modified to inquire about the past year, and will be administered at baseline. The AUDIT will be used to characterize the sample.
- *Clinician-Administered PTSD Scale for DSM-IV (CAPS)*:⁸⁶ The 17-item CAPS uses a structured clinical interview designed to assess the 17 symptoms of PTSD outlined in the DSM-IV. The CAPS will be used by the interviewer to make a current (past month DSM-IV diagnoses of PTSD. The frequency and intensity of each symptom on the CAPS is rated on separate 5-point scales, yielding both dichotomous and continuous scores (range = 0 to 8) for each symptom and for the disorder as a whole (range = 0 to 136). The CAPS will be used as a stratification variable for group assignment and as a secondary outcome measure and will be administered at screen, baseline (to be done at baseline only if more than 14 days has elapsed since the screen visit) and weeks 8, 13 and 19.

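### Similar missing-data patterns do not make LOCF valid in the rate-of-change ANCOVA; for PACS it usually dilutes the prazosin effect and can distort it either way

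*Combined protocol and SAP*

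**What the plan says.** Section 11.1 of the combined protocol and SAP analyses each primary outcome by a week-13 linear regression and by a repeated-measures GEE on weeks 8 and 13. It then adds a further analysis: "Secondarily, an analysis of covariance (ANCOVA) rate of change analysis will be done as a confirmatory or sensitivity analysis". Missing data are handled differently for each:

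- GEE: "For the GEE analysis no imputation strategy is required".
- Rate-of-change ANCOVA, first step: "For the ANCOVA analysis the missing data patterns will be evaluated between the treatment groups".
- First branch: "If the patterns are similar and the magnitude of missing data is small, a conventional last observation carried forward (LOCF) imputation will be performed".
- Second branch: "If the amount of missing data is substantial and/or the patterns of missingness disparate", the Dawson summary-statistic method is used. It fits a slope per participant, stratifies on the missing-data pattern, and is described as robust to non-ignorable missingness.

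No test, margin or threshold defines similar, small or substantial. Section 11.1 expects that retrieving dropouts will "result in a limited number of missing observations". Section 11.2 plans on heavy loss from treatment: "Assuming an approximately 40% dropout rate, we will randomize 200 participants to have 120 study completers".

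The measurement schedule matters here. Section 10.2 says: "The PACS will be administered at baseline and on weeks 8, 13 and 19". The alcohol use calendar, by contrast, is completed at every visit (10.1, 10.2).

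**The concern.** The rule treats matching patterns and little missing data as grounds for LOCF. Matching patterns show only that the arms lost people in similar ways. They do not show that a participant's last recorded value is a fair stand-in for the week-13 value. With PACS, someone who leaves before week 8 and is not reached again has only the baseline score, so a rate-of-change analysis counts that person as not having changed.

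This has two consequences. With equal loss in the two arms, the zero changes dilute a true drug effect. With unequal loss, they also mix in any improvement that both arms share. Such improvement is plausible, because everyone is receiving alcohol treatment. The arm that loses more people early then looks worse than it is.

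At stake is the value of an analysis meant to confirm the primary result. It could fail to confirm a real effect, or misstate its size, because of the imputation.

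**Working it through.** **Plan's own figures.** Randomised number: 120 / (1 − 0.40) = 200, or 100 per arm at 1:1. PACS power (11.2): the pilot changes are −2.6 (SD 5.8) and −0.3 (SD 3.3), a difference of −2.3. Root-mean-square SD = √((5.8² + 3.3²)/2) = 4.72. With 60 per arm, z = (2.3/4.72) × √30 − 1.96 = 0.71, which gives 76%. Both figures reproduce.

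**Formula.** Let δ be the true effect, C the improvement shared by both arms, and dP and dC the proportions missing on prazosin and placebo. Assume all missingness starts before week 8, is unrelated to outcome and is not retrieved. Leavers contribute zero change (and zero slope), so the expected LOCF difference is

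(1 − dP)(C + δ) − (1 − dC)C = (1 − dP)δ + (dC − dP)C.

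The first term is dilution. The second can have either sign.

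**Estimates with δ = 0.40 SD.** The simulated column assumes 100 per arm, correlation 0.6 between all visits, and similarity read as chi-square p>0.05 on the proportions missing. It keeps only trials judged similar.

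| Missing, prazosin / placebo | Formula at C = 0, 0.5, 1.0 SD | Simulated, given similar |
|---|---|---|
| 5% / 5% | 0.38, 0.38, 0.38 | about 0.38 |
| 15% / 15% | 0.34, 0.34, 0.34 | about 0.34 |
| 20% / 10% | 0.32, 0.27, 0.22 | 0.33, 0.30–0.31, 0.27 |
| 10% / 20% | 0.36, 0.41, 0.46 | 0.35, 0.38, 0.41 |

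Example, third row at C = 1.0: 0.80 × 0.40 − 0.10 × 1.0 = 0.22. The simulated values are less extreme because trials with the widest gaps in missingness are screened out. Analysis of observed values recovers about 0.40 SD.

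**Power of the LOCF slope analysis.** The comparator is a baseline-adjusted ANCOVA on observed week-13 values. It is not a slope fit, so the contrast is approximate.

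- 20% prazosin / 10% placebo: about 89% at C = 0, falling to about 61–64% at C = 1.0 SD, against about 90%.
- 15% in each arm: 84–93%, against 89–90%.
- 5% in each arm: 91–94%, against 92–93%.
- No drug effect: rejection stays at 4–8%. The main harm is a wrong effect size and lost power, not false positives.

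**On the PACS scale.** Use δ = −2.3 and the pilot placebo change, C = −0.3:

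- 5% in each arm: 0.95 × (−2.3) = −2.19, a 5% loss.
- 10% in each arm: 0.90 × (−2.3) = −2.07, a 10% loss.
- 10% prazosin, 5% placebo: 0.90 × (−2.6) − 0.95 × (−0.3) = −2.06, an 11% loss.

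If both arms instead improved by an assumed 6 points:

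- 10% prazosin, 5% placebo: 0.90 × (−8.3) + 0.95 × 6 = −1.77, a 23% loss.
- 5% prazosin, 10% placebo: 0.95 × (−8.3) + 0.90 × 6 = −2.49, an 8% inflation.

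**The case against.** The strongest reply is that the rule limits LOCF to cases where it does little harm, and that the plan works to keep missingness low. Much of this stands.

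- LOCF needs both conditions, similar patterns and small missingness. A reader might infer that it applies whenever patterns look similar; the text does not say so. At the planned 40% dropout, the natural route is the Dawson method unless retrieval succeeds.
- Retrieval is planned. Section 13.6 has week-13 assessments performed for participants who terminate early because they cannot tolerate the minimum dose, and 11.1 provides telephone interviews and mailed questionnaires. If half of the early leavers were assessed (an assumption), slope power in the 20% / 10% case would be 92, 88 and 83% at C = 0, 0.5 and 1.0 SD. The same run without retrieval gave 88, 77 and 62%.
- The pilot placebo change in PACS was only −0.3, so the 1 SD improvement is the unfavourable end of an assumed range.
- A reader might infer that the similarity check often misses a real dropout difference. That presumes a significance test. Section 11.6 names chi-square for completion of the medication phase, but nothing ties it to this decision. Under that assumed test, about 47–49% of trials with true missingness of 20% and 10% would pass as similar; the documents do not support a miss rate for the plan as written.
- A reader might also infer that LOCF always shrinks the effect. The reversed split shows otherwise.

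What the reply does not answer is that equal missingness does not remove the dilution. With 15% in each arm the estimate is 0.34 SD however well the patterns match. Successful retrieval is also what makes the LOCF branch the likely one.

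**Conclusion.** The point holds as a weakness in a stated method for a secondary analysis. LOCF usually dilutes the PACS effect and can distort it in either direction, and the pattern comparison does not guard against this. The size runs from slight (about 0.38 against 0.40 SD at 5% missing per arm) through moderate (0.34 SD at 15% per arm) to material (0.33 to 0.27 SD at 20% prazosin and 10% placebo). With placebo losing more, the estimate is 0.35 to 0.41 SD.

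These figures rest on the assumed effect, correlation, missingness, shared improvement and chi-square reading, none of which the documents give for this purpose. They describe PACS. The calendar is less exposed because a leaver before week 8 may have later entries to carry. A reader might infer that the primary results are compromised; the documents do not support that, since neither the week-13 regression nor the GEE is assigned LOCF. The change is worth making because the analysis is meant to confirm the primary result and the remedy is cheap.

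**What to change.** In 11.1, delete the LOCF sentence. In that branch, fit the rate-of-change analysis to all observed values with a likelihood-based mixed model containing time as a slope, treatment, treatment-by-time, the baseline value and the stratifying variables. Multiple imputation by arm is an acceptable alternative; name one of the two in advance.

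Keep the Dawson pattern-stratified method as the sensitivity analysis for non-ignorable missingness. Report missingness by arm and visit as a descriptive table, giving the between-arm difference with its 95% confidence interval, so that it no longer licenses LOCF.

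The cost is SAP wording and a standard procedure, with no new data or participants. The small downside is that the replacement relies on data being missing at random, which is why the Dawson method should stay.

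### The pattern-stratified slope test is called robust to non-ignorable missingness without the condition it needs: that treatment does not change who falls into each pattern

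*Combined protocol and SAP*

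**What the plan says.** In Section 11.1 (Statistical Considerations) of the combined protocol and SAP, the primary outcomes are compared by a week-13 linear regression and, as a repeated-measures analysis over weeks 8 and 13, by GEE. An ANCOVA of rate of change then serves as a confirmatory or sensitivity analysis. Only this last analysis has a missing-data rule. Patterns are compared between arms. If they are alike and little is missing, LOCF is used. "If the amount of missing data is substantial and/or the patterns of missingness disparate", the Dawson summary-statistic method replaces the ANCOVA. The plan describes it so: "The approach summarizes the response profile using a least square slope, and stratifies on the missing data pattern". Its justification is one unqualified sentence: "This method has been shown to be robust to non-ignorable missingness".

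The same section analyses the secondary outcomes in a similar way. Section 11.2 plans on heavy loss: "Assuming an approximately 40% dropout rate", 200 are randomised to obtain 120 completers. Section 11.1 nevertheless expects follow-up of dropouts to leave few observations missing.

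**The concern.** The missing-data pattern is known only after randomisation. Comparing arms among those with all visits, or among those seen only to week 8, is fair under the null only if the same kind of participant enters that group in both arms. If one arm loses people for reasons tied to their drinking and the other loses them for other reasons, or at a different rate, the arms can differ within each pattern with no drug effect at all. The robustness claim needs that condition, and the plan does not state it. Disparate patterns, one of the plan's own triggers for the method, are a sign that the condition may fail.

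The terms that drive the switch (small, similar, substantial, disparate) have no thresholds, so the method is chosen after arm-specific missingness has been seen. At stake is whether an analysis meant to support the main result in the face of dropout can itself be distorted by dropout.

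**Working it through.** **Inputs from the documents.** Allocation 1:1, 200 randomised, about 40% dropout, 60 per group for power; PACS change −2.6 (SD 5.8, N=27) v −0.3 (SD 3.3, N=26); drink units 30.3 (SD 32, N=10) v 62 (SD 58, N=9) (Sections 11.2 and 11.4). Measurement at baseline and weeks 8 and 13 (Section 11.1). The plan gives no type I error for the stratified test and no strata weights.

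**The plan's own figures.** Power = Φ(δ / (s√(2/60)) − 1.96).
- Drink units: s = √[(9×32² + 8×58²)/17] = 46.1; δ = 31.7; power = Φ(3.77 − 1.96) = 96.5% (stated 97%).
- PACS: s = √[(26×5.8² + 25×3.3²)/51] = 4.74; δ = 2.3; power = Φ(2.66 − 1.96) = 75.7% (stated 76%).
- 120/(1 − 0.4) = 200.

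These reproduce. They set the scale for what follows.

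**What the slope measures.** Times 0, 8, 13 have mean 7, deviations −7, 1, 6 and sum of squares 86. A level drop D held from week 8 gives a slope of (1 + 6)D/86 = 0.081D with three points, but D/8 = 0.125D with week 8 only. The ratio is about 1.5. The strata score the same change differently, so the unspecified weights matter. Participants with baseline only have no slope.

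**First simulation, no true effect.** 5,000 trials per row, 100 per arm; within-pattern differences pooled by inverse variance; two-sided 5%. Assumptions not in the documents: SD of true 13-week change about 4.2, measurement-error SD 1.5, 30% of those missing week 13 also miss week 8, and, where missingness is outcome-related, log-odds of 1.0 per SD of slope. Simulation error is √(0.05×0.95/5000) = 0.3 points.

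| Missing week 13, placebo/prazosin (%) | Link to outcome | Stratified | Same slopes, unstratified |
|---|---|---|---|
| 40/40 | none | 5.2% | 4.9% |
| 41/41 | same in both arms | 5.3% | 4.7% |
| 30/50 | none | 6.1% | 5.5% |
| 36/46 | same strength, rates differ | 8.3% | 5.0% |
| 30/50 | same strength, rates differ | 16.2% | 4.7% |
| 20/60 | same strength, rates differ | 48.6% | 5.4% |
| 30/50 | placebo only | 6.7% | 6.4% |
| 41/40 | placebo only | 11.9% | 6.6% |
| 41/41 | opposite directions | 33.8% | 11.9% |

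In the three rows where only the rates differ, the unstratified test of the same slopes stays near 5%, so stratification causes the excess there.

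The bias can go either way. In the outcome-related 30/50 row with equal strength, the mean slope difference is −0.052 per week; over 13 weeks that is −0.68 points in favour of prazosin, about 30% of the 2.3-point PACS planning difference. In the 41/40 row it is +0.038 × 13 = +0.49 points against prazosin.

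In the last two rows the rates are almost equal, and a chi-square comparison of pattern frequencies was significant in only about 5% of trials. Comparing frequencies does not show whether the required condition holds.

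**Second model, no true effect.** 100 per arm, pairwise correlations 0.5, 0.5 and 0.6 among baseline, week 8 and week 13, 15% lost before week 8, 3,000 to 4,000 trials per scenario:
- same mechanism in both arms: 4.9–5.7%;
- 30% v 50% missing, unrelated to outcome: 5.2–5.3%;
- opposite dependence on the week-8 value, log-odds 1 per SD: 25% with sample-size weights, 9% with inverse-variance weights;
- placebo-only dependence on week 8, log-odds 1.5: 12% and 6% with the same two weightings;
- dependence on the unseen week-13 value, differing by arm: stratified test about 6–21%, likelihood repeated-measures model about 18–58%.

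**The case against.** The strongest reply has four parts.

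First, a reader might infer that the plan uses this test only when patterns differ, and so has the rule backwards. The text does not say that. The trigger is amount and/or disparity, and with much missing but the same mechanism in both arms the test holds its level. This stands.

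Second, a reader might equate the 40% with missing outcomes. It is loss of completers, and Section 11.6 defines completion by visit attendance. Section 11.1 plans follow-up of dropouts and telephone and mail assessment. Section 13.6 has the week-13 assessments done when a participant ends early for not tolerating the minimum dose. All this may shrink the problem and stands as a limit on its size. It does not supply the missing condition, and the plan does not say how a final assessment taken early would enter the slope.

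Third, a reader might infer that a likelihood model would be safe. It keeps its level (4.4–5.8%) when dropout depends on the observed week-8 value, which is ignorable missingness. Under arm-different dependence on the unseen week-13 value it did worse than the stratified test. This stands, and it shapes the fix.

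Fourth, the main inference rests on the week-13 regression and GEE, and no decision rule hangs on this analysis. This also stands.

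**Conclusion.** The robustness sentence is wrong as written for one of the plan's own triggers. The stratified test keeps about 5% when the mechanism is the same in both arms, and about 5–6% when rates differ without any link to outcome. When outcome-related missingness differs by arm, it rejects a true null in about 6–25% of trials, rising to 34% and 49% in the two most extreme scenarios. These rates are illustrative: they show direction and range, and depend on the assumed mechanism, its strength and the strata weights.

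The effect is confined to the confirmatory or sensitivity analysis and to secondary outcomes handled similarly. A reader might infer that every disparity yields false positives, or that this rule could by itself produce a falsely positive trial. The documents support neither. The change should be made, but it does not undermine the design.

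**What to change.** In Section 11.1:
- Delete the robustness sentence, or state its condition: under the null, treatment does not change who falls into each pattern.
- Remove the data-driven choice between LOCF and the Dawson method.
- Prespecify one sensitivity analysis whatever the patterns turn out to be: multiple imputation by arm, using baseline, strata and observed follow-up, followed by delta-adjusted (tipping-point) repeats in which delta varies by arm. The delta step is essential, because imputation alone is also biased when non-ignorable missingness differs by arm, and can be more biased than the test it replaces.
- If the stratified slope test is kept, report it as supportive only, with its same-mechanism condition and its strata weights stated.

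The cost is SAP wording and some programming. No new data are needed.
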